# 1.3.3 Continuous Glucose Monitoring

CGM will be used in this study to enable real-time display of glucose values. Subjects will wear a blinded Dexcom G6 Professional (Dexcom G6 Pro) between screening and randomization and during the last 10 days of the study, in addition to their own personal CGM. Subjects will be provided training in the clinic for how to operate the Dexcom G6 Pro. Additionally, subjects will measure their glucose throughout the study using an unblinded CGM system (sensors, transmitter) and glucose meters, if required.

Subjects will also be instructed to measure glucose values using a blood glucose meter (self-monitored blood glucose [SMBG] value), as required by their personal CGM system, and to confirm glucose levels when their CGM is <70mg/dL and anytime their CGM reading does not match their symptoms or expectations.

Use of CGM is associated with a low risk for developing a local skin infection at the site of the CGM sensor placement. Itchiness, redness, bleeding, and bruising at the insertion site may occur as well as local tape allergies. CGM sensors may fracture in situ on rare occasions. In the rare instances when this has occurred in the past, consulting physicians and surgeons have recommended not to remove the wire fragment from beneath the skin as long as there are no symptoms of infection or inflammation. In the event that signs and/or symptoms of infection or inflammation arise such as redness, swelling, and pain subjects should consult with the Investigator or prescribing physician for the best course of action. If there is no portion of the

Confidential Page 19 of 70

broken sensor wire fragment visible above the skin, attempts to remove it without medical guidance are not advised.

For a complete list of risks for Dexcom G6, refer to the Dexcom G6 Pro User Guide (Dexcom 2020). For a complete list of risks for the subject's personal CGM that they will continue to use during the study, refer to the corresponding user guide.

Confidential Page 20 of 70

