- e. Subjects will be asked to provide a recent negative COVID-19 test (if available), confirm they have no symptoms of COVID-19, or provide evidence of COVID-19 vaccination.
- f. Subjects should use their study provided blood glucose meter to take an SMBG value if their CGM reading is <70 mg/dL or if their CGM reading does not match their symptoms or expectations. Hypoglycemic episodes will be defined as all SMBG measurements <70 mg/dL. See Section 3.9.2.6.
- g. A negative urine pregnancy test is required for enrollment, from all female subjects of child-bearing potential. After enrollment, additional pregnancy tests may be conducted as needed at the discretion of the Investigator.
- h. A documented normal level within 6 months of screening can be used in lieu of testing.
- i. CGM reports and pump reports will be downloaded from V1 to V2 at V2, V2 to V9 and 10 days before V9 to V9 at V9, V9 to 30 days after V9 at V13, and 30 days before V14 to V14 and V13 to V14 at V14 using Carelink for Medtronic CGM and pumps. CGM reports/data and pump reports/data will be downloaded from V1 to V2 at V2, V2 to V9 and 10 days before V9 to V9 at V9, V9 to 30 days after V9 at V13, and 30 days before V14 to V14 and V13 to V14 at V14 using Clarity for Dexcom CGM and t:connect for Tandem pumps. The site will de-identify all reports and data.
- j. Subjects in the Afrezza + AID group will be instructed not to enter carb intake/meal announcements in the pump system. In the event that they accidentally enter carb intake/meal announcement for a certain meal, they should NOT dose Afrezza for that same meal. If they accidentally take Afrezza with a meal announcement, carbs or glucagon should be administered. For subjects in the Afrezza + AID group, the site will confirm at every visit (phone or in person) to make sure they are not entering carb intake/meal announcements in the pump system.
- k. Only applies to subjects in the Afrezza + Insulin Degludec group who use a Medtronic 670G/770G system.

Confidential Page 40 of 70

Table 4: CGM/Pump Reports and Data to be Downloaded

| Reports/Data to be Downloaded                 | V2 | V9 | V13 | V14 |
|---|----|----|-----|-----|
| Blinded G6 PRO Data                           | X  |    |     | X   |
| V1 to V2 CGM/pump report/data                 | X  |    |     |     |
| V2 to V9 CGM/pump report/data                 |    | X  |     |     |
| V9 minus 10 Days to V9 CGM/pump report/data   |    | X  |     |     |

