## 3.7.2.1 Meal Challenge

Subjects will come into the clinic in a fasting state for Visit 2, with exception of treating hypoglycemia. Fasting will be defined as no intake of drink or food, with exception of water, for  $\geq$ 6 hours before the clinic visit. Subjects will also be instructed not to administer manual bolus doses of insulin during the 4 hours immediately preceding the meal challenge. If the subject requires a manual bolus insulin dose to correct hyperglycemia within the 4 hours prior to the scheduled visit, the meal challenge will need to be rescheduled.

The CGM glucose value will be confirmed 15 minutes before the start of the meal. If the subject's CGM value is  $\geq$ 70 mg/dL, the subject can start the meal challenge 15 minutes later. If the subject's CGM value is  $\leq$ 70 mg/dL, the Investigator can provide 15 g of fast-acting carbohydrates and reassess the CGM glucose value after 30 minutes and if the subject's new CGM value is  $\geq$ 70 mg/dL, the subject can start the meal challenge 15 minutes later. The CGM value obtained immediately before the start of the meal (defined as t=0) will serve as the baseline glucose value for that visit.

Subjects in the Afrezza groups will receive training on how to use the Afrezza Inhaler using BluHale technology, as well as how to identify and manage any events of hypo and hyperglycemia.

In addition to CGM, subjects will be instructed to take SMBG measurements 15 minutes before the start of the meal, immediately before the start of the meal (t=0), and at 15, 30, 45, 60, 90, and 120 minutes after the start of the meal challenge.

Confidential Page 45 of 70

mannkind

The meal challenge will consist of 1-2 bottles of Boost nutritional shake (1 bottle is approximately 240 calories, 41 g carbohydrate, 10 g protein, and 4 g fat). The meal is to be fully consumed within 15 minutes. Each Afrezza dose will be administered at the start of the meal challenge. The RAA dose will be administered  $10 \pm 5$  minutes (per label) before the start of the meal challenge, per Investigator discretion.

For Afrezza doses exceeding 12 units, inhalations from multiple cartridges are necessary. To achieve the required total mealtime dose, subjects should use a combination of 4-unit, 8-unit, and 12-unit cartridges.

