### 3.9.2.6 Hypoglycemic Events

A hypoglycemic episode is defined as any event with SMBG <70 mg/dL (i.e., Level 1 hypoglycemia) or SMBG <54 mg/dL (i.e., Level 2 hypoglycemia) (ADA 2021a) on the study-provided glucose meter. Severe hypoglycemic events are defined as events requiring assistance of another person to actively administer carbohydrate, glucagon, or other resuscitative actions. Severe hypoglycemic events will be documented as SAEs in the CRF. Nonsevere hypoglycemic events will not be documented as AEs but will be recorded in the hypoglycemia page of the CRF.

After the standardized meal challenge at Visit 2, subjects will be monitored for signs of hypoglycemia. Subjects exhibiting signs of hypoglycemia will be treated as appropriate (e.g., provided with a snack or glucose). The type of treatment given and time will be recorded and subjects will remain in-clinic until hypoglycemia is resolved.

In the event that the subject accidentally enters carb intake/meal announcement for a certain meal and also doses with Afrezza, carbohydrates or glucagon should be administered. The subject should be instructed to contact the Investigator and site staff as soon as possible following the event to ensure prompt review and to give the Investigator the opportunity to address any further necessary measures for correction.

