### 5.4.1 Safety Endpoints

- Event rates and incidence Level 1 (<70 mg/dL) and Level 2 (<54 mg/dL) hypoglycemic events as confirmed by SMBG
- Event rates and incidence of severe hypoglycemic events, defined as events requiring assistance of another person to actively administer carbohydrate, glucagon, or other resuscitative actions
- Incidence and severity of AEs: TEAEs, SAEs, AESIs, and device complaints
- Change in FEV1 from screening to end of study

Confidential Page 62 of 70

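### Table 3 footnote f counts each SMBG reading below 70 mg/dL as an episode, Section 3.9.2.6 counts events without defining one, and no document says when repeat readings belong to the same low

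*Protocol*

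**What the plan says.** The safety endpoints in Protocol Section 5.4.1 open with "Event rates and incidence Level 1 (<70 mg/dL) and Level 2 (<54 mg/dL) hypoglycemic events as confirmed by SMBG". The hypoglycemia event rate is also in the first-listed secondary objective (Protocol Section 2.2, SAP Section 8.1).

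The counting unit is described in three places:

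- Table 3, footnote f: "Hypoglycemic episodes will be defined as all SMBG measurements <70 mg/dL". The next sentence is "See Section 3.9.2.6".
- Protocol Section 3.9.2.6: "A hypoglycemic episode is defined as any event with SMBG <70 mg/dL", with a second threshold of 54 mg/dL for Level 2, measured on the meter that the study supplies. On capture, the same section says "Nonsevere hypoglycemic events will not be documented as AEs but will be recorded in the hypoglycemia page of the CRF".
- SAP Section 8.2.4: hypoglycemia confirmed by SMBG is reported as a number of events, with no definition of an event.

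Subjects are told to take a meter reading whenever their CGM shows a value below 70 mg/dL (footnote f; Section 3.9.1.2), and no limit or interval is set for repeats. At the Visit 2 meal test, SMBG is scheduled 15 minutes before the meal, "immediately before the start of the meal (t=0), and at 15, 30, 45, 60, 90, and 120 minutes" after it starts (Section 3.7.2.1). Those values go into the Visit 2 CRF. Table 4 has the study meter downloaded at V2, V9, V13 and V14.

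**The concern.** A rate of hypoglycemic events needs a rule that says where one event ends and the next begins. The only text that says explicitly what to count is footnote f, and it counts readings. Someone who treats a low and re-checks until it clears would then contribute several episodes for one low, and the rate would partly measure how often people re-test.

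The arms are planned at 10, 10 and 5 subjects, so one frequent re-tester can move an arm's rate visibly. The Visit 2 meal test sets six post-meal readings within two hours of the first study dose, so a single dip there could be scored several times.

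**Working it through.** **No figure to reproduce.** The documents give no expected hypoglycemia rate, no event count and no power calculation. The sample size of 25 is stated not to rest on statistical methods. What follows shows how far the two definitions can diverge.

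**Step 1. The wordings side by side.** Footnote f counts measurements. Section 3.9.2.6 counts events, but gives no recovery criterion, no separation time and no merging rule. The SAP counts events and adds none of these. The cross-reference therefore leads from an explicit per-reading rule to an undefined per-event one.

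**Step 2. General size.** Let m be the mean number of SMBG readings below 70 mg/dL per low. Then

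per-reading rate ÷ per-episode rate = m.

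The documents do not give m. For illustration, assume 10 lows per subject in 90 days. Follow-up is 90/365.25 = 0.2464 patient-years, a denominator I assume because the SAP states none. The per-episode rate is 10/0.2464 = 40.6 per patient-year.

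| m (assumed) | Rate counted per reading, per patient-year |
|---|---|
| 1 | 40.6 |
| 1.25 | 50.7 |
| 1.5 | 60.9 |
| 2 | 81.2 |
| 3 | 121.8 |

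The ratio to 40.6 is m whatever number of lows is assumed.

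**Step 3. One frequent re-tester.** Keep 10 lows per subject, with m = 3 in one subject and m = 1 in the rest.

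- Arm of 5: (4 × 10 + 30)/50 = 1.4 times the per-episode count.
- Arm of 10: (9 × 10 + 30)/100 = 1.2 times.

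**Step 4. Meal test.** There are eight scheduled readings, at −15, 0, 15, 30, 45, 60, 90 and 120 minutes. A dip lasting from minute 45 to minute 120 covers the readings at 45, 60, 90 and 120, so footnote f scores 4 where one low occurred, a surplus of 3. The effect on the rate is:

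- that subject: 3/0.2464 = 12.2 per patient-year;
- an arm of 10: 3/(10 × 0.2464) = 1.22 per patient-year;
- an arm of 5: 3/(5 × 0.2464) = 2.44 per patient-year.

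The ceiling is 7 surplus counts per subject (all eight readings low), at one visit only.

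**Step 5. What is untouched.** A subject with at least one reading below 70 mg/dL has at least one episode under either rule, so the proportion of subjects affected does not change.

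**The case against.** The strongest reply is that per-reading counting is not what the trial would do. Footnote f defers to Section 3.9.2.6, and Section 3.7 says that the detailed assessment descriptions are in Sections 3.9.1 and 3.9.2. Nonsevere events go on a dedicated CRF page, sites record hypoglycemic events at each visit, and no text says that events are derived by counting downloaded readings. Read per event, the inflation is zero. The analysis is descriptive, individual data are listed, and time below 70 and 54 mg/dL from the blinded CGM does not depend on how often subjects test.

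Much of this stands. It shows that inflation is possible, not established. It does not remove the conflict, because neither Section 3.9.2.6 nor the SAP says what one event is.

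Four stronger readings are tempting but not supported:

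- **Meal-test readings certainly feed the rate.** Section 3.7.2 has hypoglycemic episodes recorded at Visit 2 and nothing excludes meal-test lows. But nothing says that each value counts, and Section 3.7.2.1 does not name the meter, while Section 3.9.2.6 requires the study's own.
- **Readings taken "as required by their personal CGM system" (Section 1.3.3) inflate the count.** Such a reading counts only if it is below 70 mg/dL, and it is then a real low.
- **Testing differs by arm.** Footnote k gives a new unblinded sensor only to Medtronic users in the degludec group. The documents do not say how often either CGM system calls for meter checks, so an imbalance is conjecture.
- **The Level 1 and Level 2 thresholds are an error.** They are nested, but consistently so in Sections 3.9.2.6 and 5.4.1. What is missing is a statement of whether the Level 1 count includes Level 2.

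**Conclusion.** The point holds as a conflict of definitions in the event rate. The one explicit rule counts readings, the section it refers to counts undefined events, and the SAP settles neither. Following footnote f literally would count one low several times and give a wrong event rate.

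The size is the factor m, which the documents do not supply. The range of 1 to 3 is an assumption, and at m = 1 there is no inflation. A reader might infer that the reported rate will be inflated by some definite multiple; the documents do not support that. The four-for-one meal-test example follows from the schedule, but it needs a dip that lasts 75 minutes under supervision and it concerns one visit.

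No significance test is affected, because none is planned. The conflict should still be resolved before the data are summarized: it touches a listed objective, the arms are small and the correction is cheap.

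**What to change.** Replace footnote f with one per-episode rule and repeat it word for word in Section 3.9.2.6 and the SAP:

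- An SMBG reading below 70 mg/dL within a fixed window (for example 60 minutes) of the previous reading below 70 mg/dL belongs to the same episode. A later low reading starts a new one.
- The lowest value in the episode sets its level. The SAP states whether the Level 1 count includes Level 2 episodes.
- Counting starts at the start of the V2 meal challenge in all arms.
- Episodes detected only by scheduled meal-test readings appear on a separate line.

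With a 60-minute window the dip in the example becomes one episode, since its readings are 15, 30 and 30 minutes apart. The window should be bounded in time and should not run until a reading of 70 mg/dL or more. No recovery SMBG is required outside the meal test, so an open-ended rule could merge lows that are days apart.

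The cost is a few sentences in the protocol and SAP and a little programming. No new data are needed, provided the meter downloads carry times. The downside is that the window is somewhat arbitrary and counts may be lower. A second window can be shown as a sensitivity check.

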### 3.7 Study Procedures

Subject consent will be obtained at screening before any clinical study procedures are performed.

Procedures will be performed at the visits indicated in the Schedule of Assessments (Table 3). A detailed description of each assessment can be found in Sections 3.9.1 (efficacy) and 3.9.2 (safety).

## **3.7.1** Screening (V1)

Subject consent will be obtained upon screening before any study procedures are performed.

The following will also be performed at Visit 1:

- Record demographics and medical history (see Section 3.9.2.1)
- Perform physical examination (see Section 3.9.2.2)
- Record height and weight (see Section 3.9.2.3)
- Record vital signs (see Section 3.9.2.4), as deemed appropriate by investigator
- Record concomitant medications
- Record smoking status and pulmonary toxin exposure
- Measure and record FEV1
- Collect blood and urine for laboratory tests (see Section 3.9.2.8)
- Perform COVID-19 screening assessment
- Place Dexcom G6 Pro CGM device in blinded mode

## 3.7.2 Randomization (V2)

When subjects return for Visit 2, blinded CGM data will be downloaded and CGM sensor wear evaluated. If CGM sensor wear time is inadequate, per the discretion of the Investigator, the Screening Period can be extended and sensor wear can be repeated once (this becomes an unscheduled visit). The subject will return to the clinic 10 days (+4 days) later and, if sensor wear is adequate and all eligibility criteria met, be randomized to study treatment and proceed with the meal challenge and Visit 2 assessments. Visit 2 should be within 4 days of the end of the final sensor wear data (i.e., the CGM sensor with adequate wear time).

The following procedures will be performed at Visit 2:

- Enrollment (if eligibility criteria are met)
- Record concomitant medications
- Record current basal insulin dosages
- Remove blinded Dexcom G6 Pro CGM

Download and de-identify data from Dexcom G6 Pro device (

Confidential Page 42 of 70

• )

mannkind

Download and de-identify of unblinded CGM reports and pump reports for Medtronic CGM and pumps (

Confidential Page 43 of 70

mannkind

Download and de-identify of unblinded CGM reports/data and pump reports/data for Dexcom CGM and t:connect for Tandem pumps (

Confidential Page 44 of 70

- )
- Subjects randomized to study treatment (Afrezza + Insulin Degludec, Afrezza + AID, or AID Control)
- Disbursement/placement of unblinded CGM sensor (only applies to subjects in the Afrezza + Insulin Degludec group who use a Medtronic 670G/770G system)
- Conduct 2-hour, in-clinic meal tolerance test
- Subjects will take their first dose of Afrezza or their dose of RAA with standardized meal challenge as described in Section 3.7.2.1.
- Record AEs
- Record any hypoglycemic episodes (see Section 3.9.2.6)
- Provide additional subject training, as needed, on CGM use, including but not limited to the
  use of alerts, interpretation of trends, interfering substances, and contraindications.
- Provide study treatment instructions to the subject. Subjects in the Afrezza + AID group should be instructed NOT to enter carb intake/meal announcements into their insulin pump during the study, to avoid the risk of an automated insulin bolus (i.e., to avoid stacking insulin). In the event that they accidentally enter carb intake/meal announcement for a certain meal, they should NOT dose Afrezza for that same meal. In the event they accidentally enter carb intake/meal announcement for a certain meal and take a dose of Afrezza for that same meal, they should ingest carbohydrates or administer glucagon and contact the study team as soon as possible.
- Provided adequate training on the appropriate use of glucagon emergency kits to all subjects.

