repeated once and this becomes an unscheduled visit. The subject will return to the clinic 10 days (+ 4 days) later, and if the sensor wear is adequate and all eligibility criteria are met, be randomized to study treatment and proceed to the meal challenge and other Visit 2 assessments.

Subjects will be randomized in a 2:2:1 ratio to the following treatment groups, with the goal of 25 subjects enrolled:

- Afrezza + AID (N=10)
- Afrezza + Insulin Degludec (N=10)
- AID Control (N=5)

In order to achieve balanced representation of Medtronic 670G/770G and Tandem Control IQ AID users for each group, the randomization will target for a minimum number of subjects who use each AID system as follows:

- Within each Afrezza group (Afrezza + AID, Afrezza + Insulin Degludec):
  - o 3 subjects using Medtronic 670G/770G
  - 3 subjects using Tandem Control IQ AID
- Within the AID Control group:
  - 2 subjects using Medtronic 670G/770G
  - 2 subjects using Tandem Control IQ AID

Subjects will come to the clinic fasting with no manual insulin bolus administered within the prior 4 hours. CGM reports and pump reports will be downloaded from V1 to V2 using Carelink for Medtronic CGM and pumps, CGM reports/data and pump reports/data will be downloaded from V1 to V2 using Clarity for Dexcom CGM and t:connect for Tandem pumps. The site will deidentify all reports and data. Subjects will undergo a 2-hour meal tolerance test in the clinic. The Afrezza + Insulin Degludec and the Afrezza + AID groups will receive an Afrezza initial dose that is 2 times the calculated RAA dose (based on their insulin-tocarbohydrate ratio [I:CHO] calculated prandial dose) rounded down to the nearest 4-unit dose of Afrezza, but not exceeding 24 units of Afrezza. The Afrezza dose will be administered at the start of the meal challenge. The AID Control group will administer bolus insulin  $10 \pm 5$  minutes (per label) prior to the meal, per Investigator discretion. The start of the meal will define t=0. Subjects in the Afrezza + Insulin Degludec group will continue on AID throughout the meal tolerance test and then transition to insulin degludec at the discretion of the Investigator. Basal insulin doses and time of administration in all study subjects will be documented. Subjects should have glucagon available for use in the event of hypoglycemia

Confidential Page 6 of 70

and should not be discharged until hypoglycemia is resolved.

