- ). The site will de-identify all reports and data. Subjects will undergo a 2-hour meal tolerance test in the clinic. The Afrezza + Insulin Degludec and the Afrezza + AID groups will be administered an Afrezza initial dose that is 2 times the calculated RAA dose (based on their insulin-to-carbohydrate ratio [I:CHO] calculated prandial dose) rounded down to the nearest 4-unit dose of Afrezza, but not exceeding 24 units of Afrezza. The Afrezza dose will be administered at the start of the meal challenge. The AID Control group will administer bolus insulin  $10 \pm 5$  minutes (per label) prior to the meal, per Investigator discretion. The start of the meal will define t=0. Subjects in the Afrezza + Insulin Degludec will continue on AID throughout the meal tolerance test and then transition to insulin degludec at the discretion of the Investigator. Basal insulin doses and time of administration in all study subjects will be documented. Subjects should have glucagon available for use in the event of hypoglycemia and should not be discharged until hypoglycemia is resolved.
- Visits T3, T4, T5, T6, T7, T8 (Telephone): Between Visits 2 and 9 in the clinic, several telephone visits will be conducted. During these visits, the Investigator will titrate insulin dosages, ask about changes to concomitant medications, record any AEs and hypoglycemic events, and answer any questions/concerns raised by the subject.
- Visit 9 (Clinic): This visit will be conducted at least 30 days (+7 days) after Visit 2. CGM reports and pump reports will be downloaded from V2 to V9 and from 10 days prior to V9 to V9 using Carelink for Medtronic CGM and pumps, CGM reports/data and pump reports/data will be downloaded from V2 to V9 and from 10 days prior to V9 to V9 using Clarity for Dexcom CGM and t:connect for Tandem pump). The site will de-identify all reports and data. The Investigator will titrate insulin dosages. Basal insulin dosages will be documented.
- Visits T10, T11, T12 (Telephone): Between Visits 9 and 13 in the clinic, three telephone visits will be conducted. During these visits, the Investigator will titrate dosages and answer any questions/concerns raised by subjects.

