| Dispense glucose meter and supplies   | X                           |                |                  |    |    |    |    |    |    |      |                 |      |     |             |      |
| Provide additional glucose test strips and lancets, as necessary  |                             | X              |                  |    |    |    |    |    | X  |      |                 |      | X   |             |      |
| Collect and review glucose meter data   |                             | X              |                  |    |    |    |    |    | X  |      |                 |      | X   | X           | X    |
| Instruct subject on logging of meal announcements and Afrezza doses, as applicable  |                             | X j |                  |    |    |    |    |    |    |      |                 |      | X   |             |      |
| Collect information on
meal announcements
and Afrezza doses, as
applicable   |                             |                |                  |    |    |    |    |    |    |      |                 |      |     | X           |      |

Page 37 of 70

| Study Period   | Screen                         |    | Treatment Period |    |    |    |    |    |    |      |                 |      |     |             |      |
|--|--------------------------------|----|------------------|----|----|----|----|----|----|------|-----------------|------|-----|-------------|------|
| In-clinic Visit (V) Telehealth Visit (T)   | V1                             | V2 | Т3               | T4 | T5 | Т6 | Т7 | Т8 | V9 | T10  | T11             | T12  | V13 | V14         | ET c |
| Day  | Up to 28 Days                  | 0  | 1                | 2  | 4  | 7  | 14 | 21 | 30 | 37 b | 44 b | 51 b | 80  | 90
(EOT) |      |
| Visit Window (Days)  | Before
Random. a |    |                  |    |    | ±2 | ±2 | ±2 | +7 | ±2   | ±2              | ±2   | +2  | +7          |      |
| First dose of Afrezza
(Afrezza groups) or
dose of RAA (AID
Control group) with
standardized meal   |                                | X  |                  |    |    |    |    |    |    |      |                 |      |     |             |      |
| Titration of all insulins to glycemic effect   |                                |    | X                | X  | X  | X  | X  | X  | X  | X    | X               | X    | X   |             |      |

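### The instruction not to announce meals to the pump leaves out the Afrezza + Insulin Degludec group, which takes its first Afrezza dose with AID running at the Visit 2 meal challenge

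*Protocol*

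**What the plan says.** The precaution has two parts: do not enter carbohydrates or a meal into the pump, and if a meal was entered by mistake, do not take Afrezza for it. Section 3.7.2 of the protocol gives it at Visit 2: "Subjects in the Afrezza + AID group should be instructed NOT to enter carb intake/meal announcements into their insulin pump during the study". Table 3 footnote j repeats it: "Subjects in the Afrezza + AID group will be instructed not to enter carb intake/meal announcements in the pump system". The Table 3 reminder row, section 3.7.3 (T3 to T8) and section 3.7.4 (Visit 9) repeat the do-not-announce part for the same group.

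In Table 3 the reminder row starts at T3. At Visit 2 the precaution enters through footnote j, which is attached to the Visit 2 cell of the row "Instruct subject on logging of meal announcements and Afrezza doses, as applicable".

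The Afrezza + Insulin Degludec group does not come off its pump before the Visit 2 meal. The Synopsis says: "Subjects in the Afrezza + Insulin Degludec group will continue on AID throughout the meal tolerance test". Section 3.1 says that these subjects "will continue on AID throughout the meal tolerance test and then transition to insulin degludec at the discretion of the Investigator".

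Under section 3.4.4 both Afrezza groups take the same first dose at that meal: twice the calculated rapid-acting analog (RAA) dose, rounded down to a 4-unit step and capped at 24 units. Section 3.7.2 makes Afrezza and RAA alternatives: "Subjects will take their first dose of Afrezza or their dose of RAA with standardized meal challenge".

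**The concern.** At the Visit 2 meal the two Afrezza groups are in the same position: a first Afrezza dose, an AID pump running, and at least 3 months' experience of AID (inclusion criterion 4). Section 1.2 describes hybrid systems as automated basal delivery with manual mealtime boluses. Dealing with the pump at a meal is therefore an established habit for these subjects. The sponsor saw the hazard and wrote a precaution, but it reaches one of the two groups.

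At stake is hypoglycemia at one meal per subject. If a subject in the degludec group announced the challenge meal, the pump could deliver a meal bolus on top of Afrezza. Section 1.1 puts the return to near baseline at about 180 minutes for inhaled insulin and about 5 hours for RAA. Section 3.7.2.1 requires 2 hours of supervision after the Afrezza dose. The action of a mistaken pump bolus could outlast that period, and the rule against discharge applies only while hypoglycemia is present.

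**Working it through.** The protocol gives no figure to reproduce. The main check is to set the texts side by side.

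**1. Who is told not to announce meals?** Section 3.7.2, footnote j, the Table 3 reminder row, section 3.7.3 and section 3.7.4 all name Afrezza + AID and no other group.

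**2. Who takes Afrezza with AID running?** Afrezza + AID does so throughout. Afrezza + Insulin Degludec does so at the Visit 2 challenge (Synopsis, 3.1, 3.4.4). That is 10 of 10 + 10 = 20 planned Afrezza subjects, with 10 × 1 = 10 planned overlap meals.

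**3. Does any other text fill the gap for the degludec group?**

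| Safeguard | Reaches the group? | Covers announcing the challenge meal? |
|---|---|---|
| No manual bolus in the 4 hours before the challenge (3.7.2.1) | Yes, no group named | Not clearly; it covers the time before the meal |
| Reschedule after a correction bolus (3.7.2.1): "within the 4 hours prior to the scheduled visit, the meal challenge will need to be rescheduled" | Yes | No; it concerns a bolus before the visit |
| Correction doses no sooner than 60 to 90 minutes after Afrezza, or per Investigator discretion (3.4.4) | Yes | No; it covers corrections |
| Training on hypo- and hyperglycemia (3.7.2.1) | Yes | Not stated |
| 8 SMBG time points, 2-hour supervision, glucagon available (3.7.2.1) | Yes | No; these detect and treat |
| Action after announcement plus Afrezza (3.9.2.6) | Yes, worded for any subject | No; it is rescue |

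No row gives the instruction not to announce, or the rule to withhold Afrezza.

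**4. How large would a double dose be?** This is an illustration. It assumes that the meal is announced, that the pump delivers the full calculated dose D, and an I:CHO that the documents do not give. Inputs from the protocol:
- Meal: 1 to 2 bottles, and "1 bottle is approximately 240 calories, 41 g carbohydrate, 10 g protein, and 4 g fat", so 41 g or 82 g of carbohydrate.
- Afrezza dose A: 4 U if D < 4 (Table 2); otherwise 2D rounded down to a multiple of 4, at most 24 U.
- Equivalence: 1.5 to 2 Afrezza units per RAA unit (section 1.2).

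Total in RAA-equivalent units = D + A/2 to D + A/1.5.

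| Assumed I:CHO | Meal | D (U) | A (U) | Total | Total ÷ D |
|---|---|---|---|---|---|
| 1 U per 5 g | 41 g | 8.2 | 16 | 16.2–18.9 | 1.98–2.30 |
| 1 U per 10 g | 41 g | 4.1 | 8 | 8.1–9.4 | 1.98–2.30 |
| 1 U per 15 g | 41 g | 2.73 | 4 | 4.7–5.4 | 1.73–1.98 |
| 1 U per 5 g | 82 g | 16.4 | 24 | 28.4–32.4 | 1.73–1.98 |
| 1 U per 10 g | 82 g | 8.2 | 16 | 16.2–18.9 | 1.98–2.30 |
| 1 U per 15 g | 82 g | 5.47 | 8 | 9.5–10.8 | 1.73–1.98 |

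Over D from 2 to 16 U, the lowest multiple is just below D = 4, where A = 4: (4 + 4/2)/4 = 1.50. The highest is where 2D is an exact multiple of 4, such as D = 4: (4 + 8/1.5)/4 = 2.33. The error would therefore give roughly one and a half to two and a third times the calculated dose. The documents give no probability for it, so no event count can be derived.

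**The case against.** The strongest reply is that the precaution names the group with lasting exposure. Afrezza + AID subjects manage their own meals on a pump for about 90 days, while the degludec group has one clinic meal on it. That meal is closely watched, all subjects are trained on glucagon, and section 1.3.2 adds clinic training and frequent calls in the first 21 days. The intended dosing is clear: Afrezza or RAA, not both. All of this stands, and it is why the point is graded low. It does not supply the instruction, though. If the either/or dosing wording were enough, the explicit instruction to the Afrezza + AID group would be redundant too.

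A second reply is that the ban on manual boluses in the 4 hours before the challenge already prevents the error. It helps in part: given the description of hybrid systems in section 1.2, a meal bolus entered shortly before the challenge arguably breaches it. But section 3.7.2 calls the bolus that follows an announcement automated. The AID Control group's own dose is also timed 10 ± 5 minutes before the meal, so the ban cannot be meant to cover the challenge meal's own bolus in every group. An announcement at or after the start of the meal is clearly outside it.

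A reader might infer that the degludec group has no protection against stacking, or that the protocol lets these subjects take both doses. The documents do not support either reading: several precautions reach the group, and Afrezza alone is the written dose. A reader might also infer a run of unsupervised meals at home on pump and Afrezza together. The switch has no fixed time, but the text places it straight after the meal test and Table 3 dispenses degludec at Visit 2. No later overlap is planned.

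**Conclusion.** The point holds as a narrow gap in prevention. Ten of 20 planned Afrezza subjects take a first dose with AID running and are not covered by the do-not-announce and withhold instruction. The planned exposure is one supervised meal each; any overlap before the pump is stopped is unplanned and cannot be counted. Rescue after the error is covered for everyone.

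The wording gap rests only on the current protocol text. The size of a double dose, 1.5 to 2.33 times the calculated dose for D from 2 to 16 U, rests on the equivalence in section 1.2 and on full delivery of the pump bolus. How often the error would happen is unknown, so a claim that hypoglycemic events should be expected from it would go beyond the documents. The HbA1c and CGM analyses are not affected. The grade is CONSIDER: an improvement at almost no cost.

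**What to change.** In section 3.7.2 and Table 3 footnote j, replace the opening reference to the Afrezza + AID group with: *Any subject taking Afrezza while an AID pump is running (including the Afrezza + Insulin Degludec group at the V2 meal challenge and until the pump is stopped)*. The rule to withhold Afrezza for an announced meal follows in the same text and then applies to both groups. State that the instruction is given before the Visit 2 meal; in the section 3.7.2 list it comes after the meal-challenge items.

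I would not add a rule that forces the challenge to be rescheduled if the meal is announced. It would act after randomization, and the protocol would then have to settle whether Day 0 moves, how the 4-day limit after sensor wear applies, and which regimen the subject follows meanwhile. A separate T3 reminder for the degludec group is not needed either, because no later overlap is planned and the new wording runs until the pump is stopped.

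The cost is a minor wording amendment and a note to sites, with no added visits, subjects or data fields.
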